### **9.4 Laboratory Data**

Laboratory data obtained according to the schedule of assessments will be recorded on the CRF or other data collection instrument. Only laboratory data requested by the protocol should be recorded unless specific findings result in a clinical event such as an adverse event or documentation of peripheral blood count recovery. These results will be collected and recorded on the CRF.

## **10 Other Evaluations**

### **10.1 Blessed Orientation-Memory-Concentration Test (BOMC)**

This is a short six item test designed to evaluate older patients for early dementia. The assessment is not affected by age or educational level. The six-item Blessed Orientation-Memory-Concentration (BOMC) test was developed by Katzman, Brown, Fuld, et al. (1983) from the longer (29-item) Blessed Information-Memory-Concentration (BIMC) test (Blessed, Tomlinson, and Roth, 1968). Katzman and colleagues (1983) selected 6 of the original 29 BIMC items based on a series of statistical analyses. The scores from each of the six items are multiplied as detailed below to yield a weighted score. Possible total scores on the BOMC range from 0 (all items answered correctly) to 28 (all items answered incorrectly). Weighted error scores greater than 10 are consistent with dementia, according to Katzman et al. (1983).

### **10.2 Montreal Cognitive Assessment (MOCA)**

The MoCA test is a one-page 30-point test administered in approximately 10 minutes. The test and administration instructions are freely accessible for clinicians at [www.mocatest.org](http://www.mocatest.org). The test is available in 35 languages or dialects. There are 3 alternate forms in English, designed for use in longitudinal settings.

The MoCA assesses several cognitive domains. The short-term memory recall task (5 points) involves two learning trials of five nouns and delayed recall after approximately 5 minutes. Visuospatial abilities are assessed using a clock-drawing task (3 points) and a three-dimensional cube copy (1 point). Multiple aspects of executive functions are assessed using an alternation task adapted from the trail-making B task (1 point), a phonemic fluency task (1 point), and a two-item verbal abstraction task (2 points). Attention, concentration and working memory are evaluated using a sustained attention task (target detection using tapping; 1 point), a serial subtraction task (3 points), and digits forward and backward (1 point each). Language is assessed using a three-item confrontation naming task with low-familiarity animals (lion, camel, rhinoceros; 3 points), repetition of two syntactically complex sentences (2 points), and the aforementioned fluency task. Finally, orientation to time and place is evaluated (6 points).

### **10.3 The Functional Assessment of Cancer Therapy – Leukemia (FACT-Leu)**

The FACT-Leu is a validated measurement of quality of life parameters for patients undergoing treatment for acute leukemia. This questionnaire is standardly used in leukemia treatment protocols to measure quality of life parameters.

### **10.4 Medical Resource Use**

Medical resource use (MRU) data will be collected for all study participants and analyzed by health outcomes (overall survival and response (CR+CRp+CRi) for CPX-351. The MRU data collected in the trial will be used to identify costs associated with planned induction and consolidation treatment and for unplanned medical interventions necessary for patient support. Specific MRU data collected will include but may not be limited to:

- hospitalization nights (general ward and intensive care);
- blood product support (PRBC, Platelets, other);
- non-chemotherapy drugs (anti-infectives, growth factors, etc.); and
- AML chemotherapy (induction vs. consolidation).

## **11 Statistical Considerations**

The primary objective of this non-randomized open label study is to evaluate the safety and efficacy of CPX-351 as a treatment for AML in elderly ( $\geq 60$  years of age) patients. Dose reductions or protocol closure will be considered:

- 1) If  $>2$  of the first 5 patients or  $>3$  of the first 15 patients experience grade 4 toxicities, accrual will stop, the protocol reviewed, and dose modifications considered. If the incidence of grade 4 toxicity exceeds 20% of patients at any point after the first 15 patients have been treated, accrual will stop, the protocol will be reviewed, and dose modifications considered.
- 2) If 30-day mortality exceeds 20% ( $>3$  of the initial 15 patients), *all further accrual will stop*. Subsequent enrollment after the first 15 subjects should ideally resume after the safety analysis is complete, however recognizing the acute nature of AML,

it might not be possible to deny treatment to subjects in screening for ethical reasons sufficiently long to evaluate safety or efficacy. In other words, if the 30-day mortality for the preceding patients is less than 20%, study accrual will continue during the DSMB's safety analysis.

In the event that more than 15 subjects have enrolled before the safety analysis, only the first 15 subjects dosed will be informative for determining need for dose reduction as outlined above.

Patients who die within the first 7 days because of leukemia related toxicity will be replaced. Those patients will be included in the analysis given the intention to treat for 30 day mortality and overall survival.

Analyses will primarily be descriptive in nature. Categorical variables will be summarized as frequency counts with associated percentages and continuous variables will be summarized as mean, standard deviation, median and range. Exact confidence intervals will be computed using the Clopper-Pearson method.

All analyses will be performed using SAS version 9.2 or higher.

Additional details regarding statistical analyses may be presented in a Statistical Analysis Plan (SAP).

## **11.1 Primary and Secondary Endpoints**

### *11.1.1 Primary Endpoints*

In the CPX-351 cohort, the primary efficacy endpoint is overall survival (OS) as defined in Section 8.2; the primary safety endpoint is the 30-day mortality rate.

### *11.1.2 Secondary Endpoints*

Secondary efficacy endpoints include complete response (CR, CRp, CRI, and CR+CRp+CRI), the relationship of cognitive function to treatment response and OS, event-free survival and morphologic leukemia free state (as defined in Section 8). Secondary safety endpoints include incidence of AEs and SAEs, laboratory measurements (hematology and biochemistry), vital signs and physical examinations.

## **11.2 Sample Size and Power Justification for Primary Endpoint**

With 24 months for accrual, and a minimum of 36 months of follow-up, using a one-sided alpha-level of 0.05, a sample size of 30 patients has 80% power to detect a difference between the null hypothesis of 10 months median survival versus 16 months median survival in this patient population.

In regards to safety, with a sample size of 30 the maximum width of the one-sided 95% exact confidence interval for estimated 30-day or 60-day mortality rates is less than 19%.

Analysis of the relationship of cognitive function to outcome and overall survival will be hypothesis generating.

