**Study Design:**

This is an open label study to assess the safety and efficacy of CPX-351 as first intensive therapy in elderly (age  $\geq$ 60 years) patients with AML with companion cognitive function testing to determine whether this contributes to outcome in these patients. Patients may have received prior AML treatment with non-intensive regimens, e.g. hypomethylating agents, low-dose cytarabine, or lenolidomide, but may not have received intensive AML treatment with anthracyclines and/or infusional cytarabine prior to enrollment on this trial. The cohort will include 30 patients treated with single-agent CPX-351. These patients will be assessed for efficacy and safety. Quality of life will be assessed using the FACT-LEU in all patients. Cognitive function will be assessed using the Blessed Orientation-Memory-Concentration Test and the Montreal Cognitive Assessment.

---

Study enrollment is expected to be completed within approximately 2 years.

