The median overall survival for patients treated with CPX-351 in the study was 9.56 months compared to 5.95 months for patients receiving 7+3, representing a 3.61 month improvement in favor of CPX-351. The hazard ratio (HR) was 0.69 (p=0.005) which represents a 31% reduction in the risk of death versus 7+3. The percentage of patients alive 12 months after randomization was 41.5% on the VYXEOS arm compared to 27.6% on the 7+3 arm. The percentage of patients alive 24 months after randomization was 31.1% on the CPX-351 arm compared to 12.3% on the 7+3 arm.

Event-free survival was also statistically significant in favor of CPX-351. The HR was 0.74 (p-value=0.021). The median event-free survival was 2.53 months in the CPX-351 arm compared to 1.31 months in the 7+3 arm.

CPX-351 also demonstrated a statistically significant improvement in induction response rate (CR+CRi of 47.7% versus 33.3%; p=0.016) and this significance was maintained for the analysis of CR alone (CR of 37.3% versus 25.6%, p=0.040).

Thirty-four percent of CPX-351 treated patients received a stem cell transplant (SCT) compared to 25% of 7+3 treated patients. In a landmark survival analysis of patients receiving a SCT, CPX-351 patients had significantly improved survival post-transplant (HR was 0.46 (p-value=0.0046)). The median overall survival had not been reached in the CPX-351 treated patients compared to 10.25 months in the 7+3 treated patients.

Thirty-day and sixty-day all-cause mortality favored CPX-351. Thirty-day mortality was 5.9% compared to 10.6% and sixty-day mortality was 13.7% versus 21.2%.

Grade 3-5 non-hematologic and hematologic adverse events were similar between the VYXEOS and 7+3 arms.

On the basis of the phase 3 trial data, CPX 351 was approved by the FDA for treatment of older patients aged 60-75 with prior myeloid hematologic disease.

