### **11.4 Analysis of Primary Endpoints**

Overall survival will be analyzed using Kaplan-Meier methods. Patients who have not died at the time of analysis will be censored on the date they were last known to be alive. Median survival and the associated 95% confidence interval will be computed using the Brookmeyer-Crowley method. The estimated survival curve will be generated.

Estimates of 30- and 60-day mortality rates will be computed using Kaplan-Meier methods along with associated two-sided 95% confidence intervals computed using the Brookmeyer-Crowley method.

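### The 80% power in section 11.2 is reproduced only by an unstated constant-hazard calculation; the survival analysis planned in section 11.4 has about 50% power at best

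*Combined protocol and SAP*

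**What the plan says.** Section 11.2 sets the design out as a hypothesis test. The setting is "With 24 months for accrual, and a minimum of 36 months of follow-up"; 30 patients and a one-sided alpha of 0.05 are then said to give "80% power to detect a difference between the null hypothesis of 10 months median survival versus 16 months median survival". It names no survival distribution, test statistic or decision rule.

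Section 11.4 gives the only planned analysis of overall survival, which is Kaplan-Meier estimation: "Median survival and the associated 95% confidence interval will be computed using the Brookmeyer-Crowley method". It makes no comparison with 10 months. Section 11 adds: "Analyses will primarily be descriptive in nature".

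Section 2.4 holds the protocol's only survival-curve information for the drug, from the phase 3 trial. On the median: "The median overall survival for patients treated with CPX-351 in the study was 9.56 months". On the tail: "The percentage of patients alive 24 months after randomization was 31.1% on the CPX-351 arm compared to 12.3% on the 7+3 arm". It also reports 41.5% alive at 12 months on CPX-351.

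**The concern.** A power figure belongs to a particular test under a particular survival model. Here neither is given, and the analysis described two sections later is of a different kind from the calculation that yields 80%. Two things are at stake.

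- If the trial is read through its planned median and interval, the chance of showing a median above 10 months when the truth is 16 is well below the stated 80%.
- If an analyst instead picks the test that matches the 80%, its validity rests on a constant hazard. The 24-month phase 3 figure does not fit that model, and follow-up of at least 36 months gives long survivors a large share of the exposure time.

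**Working it through.** **Inputs.** From 11.2: n = 30, one-sided alpha 0.05 (z = 1.645), medians 10 and 16 months, 24 months of accrual (taken as uniform), at least 36 months of follow-up. From 2.4: CPX-351 median 9.56 months, 41.5% alive at 12 months, 31.1% at 24 months.

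**1. Reproducing the 80%.** With a constant hazard λ = ln 2 / median, the probability that a death is observed is 1 − (e^(−36λ) − e^(−60λ)) / (24λ).

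- Median 10: 0.960, so 28.8 expected deaths.
- Median 16: 0.869, so 26.1 expected deaths.
- Log-hazard test with separate null and alternative variances: Φ[(ln 1.6 − 1.645/√28.8) × √26.1] = 79.8%.
- Simpler version: Φ(ln 1.6 × √26.1 − 1.645) = 77.5%. With all 30 dead: 82.4%.

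So the figure is a one-sample exponential calculation.

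**2. Power of the planned analysis.** Every patient is followed for at least 36 months, so, apart from losses, nobody is censored before month 10. The lower Brookmeyer-Crowley limit then exceeds 10 months when the Kaplan-Meier estimate at 10 months is significantly above 50%. With x of 30 alive at 10 months, z = (x/30 − 0.5) / √[(x/30)(1 − x/30)/30]:

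| Alive at 10 months | z | Above 1.645 (one-sided 95%) | Above 1.96 (two-sided 95%) |
|---|---|---|---|
| 19 | 1.52 | no | no |
| 20 | 1.94 | yes | no |
| 21 | 2.39 | yes | yes |

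A log-log transformation gives 1.37, 1.68 and 1.98, hence the same cut-offs. Exact binomial results:

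- Type I error (10-month survival 0.5): 4.9% for 20 or more alive, 2.1% for 21 or more.
- Power with a constant hazard and median 16 (10-month survival 0.5^(10/16) = 0.648): **50.0%** for the one-sided limit, **35.1%** for the two-sided interval.

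The shortfall is therefore present before any question of survival shape.

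**3. Does the phase 3 curve fit a constant hazard?** With median 9.56, a constant hazard predicts 0.5^(12/9.56) = 41.9% alive at 12 months (reported 41.5%, which agrees) and 0.5^(24/9.56) = 17.5% at 24 months (reported 31.1%, which does not). The implied hazard is −ln(0.415)/12 = 0.073 per month over the first year and −ln(0.311/0.415)/12 = 0.024 over the second.

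**4. Effect of that shape on the planned analysis (one-sided limit).**

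- Time-scaled to a median of 16: the hazard is constant up to the median, so 10-month survival is again 0.648 and power about 50%.
- Proportional hazards from a null curve with median 10: month 16 corresponds to 16 × 0.956 = 15.3 months on the phase 3 curve, where the cumulative hazard is 0.880 + 3.3 × 0.024 = 0.959. The hazard ratio is 0.693/0.959 = 0.72, 10-month survival is 0.5^0.72 = 0.61, and power is 31% exactly (32% by simulation).
- Weibull with shape 0.567, which matches the median and the 24-month figure: 10-month survival exp(−0.693 × 0.625^0.567) = 0.588, power 25%. It fits 12 months less well (45% against 41.5%).

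None of these uses the curve beyond 24 months.

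**5. If the constant-hazard test were used instead.** Simulated trials of 30 (20,000 to 40,000 runs), phase 3 shape rescaled to a true median of exactly 10 months, nominal one-sided 5%. The hazard after month 24 of the phase 3 curve is my assumption, since the documents give none:

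| Assumed later hazard per month | Rejection rate when the true median is 10 |
|---|---|
| 0.073 (early hazard resumes) | 26-27% |
| 0.048 | 44% |
| 0.024 (second-year hazard continues) | 67% |
| 0.012 | 78-79% |
| 0 (flat) | 87-88% |

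With the same curve time-scaled to a true median of 16, this test rejects in about 95-97% of trials. Its raw rejection rate rises; what fails is the error rate.

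**The case against.** The strongest reply is that section 11 calls the analyses mainly descriptive and section 11.4 names no test against 10 months, so no error rate is at risk. Part of this stands. The planned Kaplan-Meier and Brookmeyer-Crowley method assumes no constant hazard and holds its error at or below 5%, while the 26-88% figures belong to a test the protocol never proposes. The reply does not rescue the 80%: section 11.2 states a null, an alternative, an alpha and a power, and the planned method does not deliver that power under any shape examined.

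A reader might infer from the phase 3 figures that survival shape is the root of the problem and that both the 80% power and the 5% error are lost together. The documents do not support that. No single test shows both failures as stated: the constant-hazard test loses the error rate but rejects more often than 80% at a median of 16, and the planned method loses the power but keeps the error rate. Confirming a constant hazard would still leave the planned analysis at about 50%.

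The phase 3 curve may also not carry over. That trial enrolled patients aged 60-75 with high-risk disease, and 34% of its CPX-351 patients were transplanted. This trial has no upper age limit, admits de novo AML and allows prior non-intensive treatment. The phase 3 shape is therefore a sensitivity case, though the only one the protocol offers.

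**Conclusion.** The concern holds in this form: the 80% describes an unstated exponential one-sample test, not the analysis in section 11.4. For the planned analysis, power is about 50% with a one-sided 95% lower limit and about 35% with a two-sided 95% interval, both under a constant hazard. The main cause is sizing by one method and analysing by another. Survival shape is a further loss only under some alternatives: about 25-32% with proportional hazards or the Weibull curve, but still about 50% if the phase 3 curve is simply stretched in time.

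The 50% and 35% rest on 30 evaluable patients, no losses before month 10, and the reading that success means a lower limit above 10 months. The lower values also assume that the phase 3 shape applies here. The inflated error of 26-88% is conditional on someone choosing a constant-hazard test and on the assumed hazard after 24 months. It is a reason to rule that test out in advance, not a defect of the analysis now written.

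**What to change.** - **Section 11.2:** state that the 80% assumes exponential survival and a parametric one-sample test. Restate power for the section 11.4 analysis as about 50% (one-sided, constant hazard), with a range of about 25-50% under survival shapes like those in section 2.4.
- **Section 11.4:** state that the 10-month null is judged by whether the one-sided 95% lower Brookmeyer-Crowley limit for the median exceeds 10 months, and not by a constant-hazard test. The interval already planned can still be reported as the descriptive estimate.

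The cost is a less favourable stated power. The change is wording only and needs no extra patients or data.

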### **11.3 Analysis Populations**

Efficacy and safety analysis populations will be comprised of all patients who receive at least one dose of study drug.

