## 7 Drug Administration

The responsibility for treatment of patients rests with the individual investigator. Protocol treatment must begin within 72 hours of registration.

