## **8 Assessment of Efficacy**

### **8.1 Efficacy Population**

All registered patients are evaluable for efficacy. Patients that die on or before Day 7 will be replaced.

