### **8.2 Overall Survival**

Overall survival is measured from the date of registration to death from any cause. Patients not known to have died will be censored on the date they were last known to be alive. Patients will be followed for up to 5 years.

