### **8.3 Event-free Survival**

Event-free survival is defined as the time from study registration to the date of induction treatment failure (persistent disease), progressive disease (PD) or death from any cause, whichever comes first. Patients alive and not known to have any of these events will be censored on the date of their last tumor assessment.

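### The efficacy population, the Day 7 replacement rule and the MLFS denominator are each stated in two ways, and both MLFS denominators leave out patients without an evaluable marrow

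*Combined protocol and SAP*

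**What the plan says.** **Efficacy population.** Section 8.1: "All registered patients are evaluable for efficacy. Patients that die on or before Day 7 will be replaced". Section 11.3: "Efficacy and safety analysis populations will be comprised of all patients who receive at least one dose of study drug". Section 11.5 divides responders by the efficacy population without saying which of the two it means.

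**Time origin.** Section 8.2: "Overall survival is measured from the date of registration to death from any cause". Section 8.3: "Event-free survival is defined as the time from study registration to the date of induction treatment failure". Section 7: "Protocol treatment must begin within 72 hours of registration". Survival status in section 6.4 is scheduled from first treatment, whereas section 4.6 counts from enrollment.

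**Replacement.** Section 8.1 replaces every death up to Day 7, whatever the cause. Section 11 is narrower: "Patients who die within the first 7 days because of leukemia related toxicity will be replaced". It continues: "Those patients will be included in the analysis given the intention to treat for 30 day mortality and overall survival". It does not mention response, EFS or MLFS for these patients.

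**MLFS denominator.** Section 8.6 takes registered patients with an evaluable post-registration marrow on or after Day 14 after the last induction. Section 11.5 takes safety-population (dosed) patients with at least one evaluable 'post-randomization' marrow and does not repeat the Day 14 condition. There is no randomization; section 11 opens with "The primary objective of this non-randomized open label study".

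**The concern.** Two analysts, one following section 8 and the other section 11, could report different denominators from the same data. For OS, the primary efficacy endpoint, the dosed-only population removes a patient who dies or deteriorates between registration and first dose, although section 8.2 has already started that patient's clock. Such losses are unlikely to be neutral, because the patients most likely to miss the first dose are the sickest.

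The replacement rules can lead to different numbers enrolled. They also leave open whether a replaced patient counts in response, EFS and MLFS.

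For MLFS, a patient who dies before a marrow is taken cannot count as a failure. Section 11 says only that a separate SAP may give further detail, so nothing in the documents settles these choices before outcomes are known in an open-label, single-arm study.

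**Working it through.** **The plan's own figure.** Section 11.2 gives 80% power with 30 patients, median OS of 10 against 16 months, one-sided alpha 0.05, 24 months of accrual and at least 36 months of follow-up. Assuming exponential survival and uniform accrual, the hazard ratio is 10/16 = 0.625. The events required are (1.645 + 0.842)² / (ln 0.625)² = 27.99. Thirty patients give 28.8 expected events under the null and 26.1 under the alternative. A simulated one-sample log-rank test has 80.5% power with averaged variance and 77.3% with null variance. The stated 80% is reproduced, and none of the definitions at issue enters it.

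The documents give no counts for what follows. Every count is an assumption chosen to show size.

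**1. Registered against dosed.** Take 30 dosed patients, 15 of them responders, and k further patients registered but never dosed.

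| k | Dosed (11.3) | Registered (8.1) |
|---|---|---|
| 0 | 15/30 = 50.0% | 15/30 = 50.0% |
| 1 | 15/30 = 50.0% | 15/31 = 48.4% |
| 2 | 15/30 = 50.0% | 15/32 = 46.9% |
| 3 | 15/30 = 50.0% | 15/33 = 45.5% |

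For OS, suppose one of 31 registered patients dies before dosing and nobody is censored before time t. Then S(t) in registered patients = (30/31) × S(t) in dosed patients. A dosed estimate of 50.0% becomes 0.968 × 50.0% = 48.4%. With k = 0 nothing changes.

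**2. Replacement.** Suppose one death by Day 7 is not due to leukemia related toxicity, and 30 other patients are enrolled under section 8.1.
- Section 8.1 replaces the death: 30 + 1 = 31 patients in total.
- Section 11 does not: 30 in total.
- If a patient is replaced under either rule, section 11 keeps that patient for 30-day mortality and OS. For response, with 15 responders among the other 30, the rate is 15/31 = 48.4% if the replaced patient is counted and 15/30 = 50.0% if not. Section 11 does not say which.

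**3. MLFS.** Under section 8.6 the state is defined on a marrow, so a patient without an evaluable one cannot be in the numerator. If x of n patients reach MLFS and m have no evaluable marrow, the reported rate x/(n − m) is at least x/n. With x = 15 and n = 30:

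| m | Rate | Exact 95% CI |
|---|---|---|
| 0 (all counted) | 15/30 = 50.0% | 31.3 to 68.7 |
| 2 | 15/28 = 53.6% | 33.9 to 72.5 |
| 4 | 15/26 = 57.7% | 36.9 to 76.6 |
| 6 | 15/24 = 62.5% | 40.6 to 81.2 |

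Two figures in the protocol help to place m. The 5.9% 30-day mortality in the phase 3 trial described in section 2.4 gives 30 × 0.059 = 1.8 deaths. The 20% in section 4.2 gives 30 × 0.20 = 6. Some patients who die by Day 30 will have had a marrow first, so as counts of early deaths these are ceilings. Non-evaluable marrows would add to m.

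**The case against.** The strongest reply is that little is at stake. The population conflict needs a patient who is registered but never dosed within a 72-hour window. Section 11 calls the analyses mainly descriptive, MLFS is a supplementary secondary endpoint, and 'post-randomization' has one sensible reading. Sections 8.6 and 11.5 agree on requiring a marrow, so that part is a choice of estimand and not a contradiction. A dosed-only efficacy population is also workable in a single-arm study if the time origin matches it. All of this stands, and it limits the point to a correction of definitions.

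Four stronger readings are tempting, and the documents do not support them:
- *The population for 30-day mortality is undefined.* Sections 9.1, 11.3 and 11.6 all define safety on dosed patients. The intention-to-treat sentence in section 11 refers to the replaced early deaths and does not set up a rival population.
- *Replacement removes early deaths from the primary analyses.* Section 11 expressly keeps them for 30-day mortality and OS. The gap is its silence on the other endpoints.
- *The MLFS timing rules clearly conflict, with a known direction.* Section 11.5 cites section 8.6 for the MLFS definition and section 11.1.2 refers back to section 8, so the Day 14 condition may be read in. Registered against dosed still differs.
- *Missing marrows also inflate the response rate.* Section 11.5 divides responders by the whole efficacy population.

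Nor do the documents establish how many patients would lack a marrow. Section 6.2 asks for marrows as needed, while Appendix 1, note 5, requires one after first induction.

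**Conclusion.** The point holds as a set of inconsistent definitions plus one denominator that favours the treatment.
- **Efficacy population:** a real conflict that reaches OS, EFS and response, but only if a registered patient is never dosed. One such patient in 31 moves a 50.0% rate by 1.6 points.
- **Replacement:** a real conflict in scope that can change the number enrolled. How replaced patients count in response, EFS and MLFS is left open.
- **MLFS:** registered against dosed differs, and leaving out patients without a marrow can only raise the rate. Two such patients move 50.0% to 53.6%, which is 3.6 points against an interval 37.4 points wide (68.7 − 31.3). Six would move it to 62.5%, a high assumption.

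These sizes rest on assumed counts; the direction of the MLFS effect does not. The sample size justification and type I error are unaffected. The definitions should be corrected before analysis, but the design is not in doubt.

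**What to change.** - Use all registered patients, including replaced ones, as the single efficacy population in sections 8.1, 8.6, 11.3 and 11.5. Start survival follow-up in section 6.4 at registration, so that an undosed patient has a schedule consistent with section 8.2.
- Reconcile the replacement rules in sections 8.1 and 11, and state that replaced patients stay in all efficacy analyses.
- Base the main MLFS rate on the efficacy population, with no evaluable marrow counted as not MLFS. Report the marrow-evaluable rate as supplementary, under one marrow-timing rule.
- Replace 'post-randomization' with 'post-registration' in section 11.5.
- Keep the dosed population for safety, including 30-day mortality, as sections 9.1, 11.3 and 11.6 already state.

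The cost is mostly wording, plus survival follow-up of any patient registered but not dosed. MLFS rates, and response rates if any patient is undosed, become slightly less favourable. The sample size does not change.
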